## 9.6 Safety Analysis

All safety analyses will be based on the Safety Population.

### 9.6.1 Analysis of Extent of Exposure

The frequencies and percentages of subjects with vaccinations will be summarized by age group and treatment group for the Randomized Population.

### 9.6.2 Solicited AEs

With the exception of redness and swelling, all solicited AEs (local and systemic) will be summarized according to severity grading scales defined in [Section 7.2](#), from “mild” to “potentially life-threatening.”

Solicited AEs will be recorded daily until 7 days post-injection within an electronic diary. The analyses of solicited AEs (any event, after any injection, and after each injection) will be performed by maximum severity and by treatment group. In addition, solicited AEs ongoing after 7 days post-injection will also be recorded as unsolicited AEs.

Frequencies and percentages of subjects experiencing each solicited AE will be presented by maximum severity. Summary tables showing the occurrence of any local or systemic solicited AE overall and at each time point will also be presented.

The severity of redness and swelling recorded as diameters (cm) will be summarized according to categories based on the largest diameter linear measurement when the local reaction is present:

- Grade 0/absent: 0 - 2.4 cm
- Grade 1/mild: > 2.5 - 5.0 cm.
- Grade 2/moderate: > 5.1 - 10.0 cm.
- Grade 3/severe: > 10.0 cm.

The following summaries of subjects will be performed:

- Solicited events by day post-injection, for each event and for any event.
- Time of first onset of solicited AEs, after injection, for each event and any event.
- Solicited AEs by maximum event severity, after injection, for each event and for any event.
- Duration of solicited AEs, after injection, for each event and maximum duration of any event.
- Solicited AEs, occurrence of at least one event by category (local, systemic), after injection.

For each of the time points or time intervals presented in the summaries, only subjects with at least one observation (ie, any non-missing values but excluding “Not done/unknown”) for the solicited AEs will be summarized.

### 9.6.3 Unsolicited AEs

All the unsolicited AEs occurring during the study will be recorded, regardless of their assessment of relatedness by the Investigator.

The original verbatim terms used by Investigators to identify AEs in the eSD will be mapped to preferred terms using the MedDRA dictionary. The unsolicited AEs will then be grouped by MedDRA preferred terms into frequency tables according to system organ class (SOC). All reported AEs, as well as AEs judged by the Investigator as at least possibly related to study vaccine, will be summarized by treatment group, according to SOC and preferred term within SOC. When an unsolicited AE occurs more than once for a subject, the maximum severity reported and strongest reported relationship to the treatment group will be counted.

---

Only TEAEs will be summarized as defined in [Section 7.1.1](#). The selection of unsolicited AEs and their assignment to time intervals will be done by day of onset and not by days ongoing/persisting.

Unsolicited AEs will be summarized by alphabetic SOC and preferred term as follows:

- Any unsolicited TEAE
- Possibly or probably related unsolicited TEAEs
- SAEs
- Possibly or probably related SAE
- Unsolicited TEAE leading to withdrawal
- Any AE leading to death

Listings of all TEAEs will be provided by subject.

#### **9.6.4 Combined Solicited and Unsolicited AEs**

Solicited AEs continuing beyond 7 days after any injection will be coded by MedDRA and combined with the unsolicited AEs. An overall summary of subjects with all combined solicited and unsolicited AEs, by SOC and preferred term, will be provided as well.

#### **9.6.5 Analysis of Other Safety Data**

The frequencies and percentages of concomitant medications will be tabulated by age group, treatment group, and overall. Medications will be coded using the WHODRUG dictionary.

### **9.7 Immunogenicity Analysis (50 to 64 years)**

#### **9.7.1 GMT/GMR**

Immunogenicity analyses will be performed by age group (50 to 59 and 60 to 64) and overall (50 to 64 years). Analyses will be performed for both OPA titers ( $\log_{10}$ ) and IgG titers (mcg/mL). All immunogenicity analyses will be based on the IEP and Exposed Population.

The GMTs and GMCs will be analyzed via linear models. The primary model is an analysis of variance (ANOVA), with logarithmically-transformed titers ( $\log_{10}$ ) as the dependent variable and treatment group and study site as the fixed effects in the model. The results included in the main tables of this report will be based on this basic ANOVA model. As a secondary analysis, in order to remove the effect of baseline concentration on the GMTs, an analysis of covariance (ANCOVA) will also be performed. The ANCOVA includes treatment group and study site as the fixed effects and  $\log_{10}$  baseline titer as the covariate in the model. The rationale for including

baseline values as a covariate is that prior data have shown vaccine response is correlated with baseline antibody levels.

The least squares means and their 95% confidence intervals (CIs) calculated based on the ANOVA and ANCOVA will be back transformed and reported as the group GMT and GMC values (adjusted for the mean baseline in the case of the ANCOVA). GMRs will also be calculated from the ANCOVA and ANOVA models.

Comparisons between relevant groups will be based on the estimated adjusted GMTs measured at Day 29 for 24 serotypes in VAX-24 (of those 20 in PCV20), and mean square error calculated from the basic ANOVA model using contrast statements. The analysis of GMFR relative to Day 1 will also be computed using similar models.

The main comparison of interest will be the three VAX-24 dose levels group versus the PCV20 (20 serotypes) group. However, the three VAX-24 dose groups will also be compared in a pairwise fashion on a serotype by serotype basis. No adjustment for multiplicity will be applied and missing data will not be imputed.

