### 9.4 Populations for Analysis

**Randomized Population:** All screened subjects who provide informed consent, provide demographic and other Baseline Screening measurements, are randomized, and are assigned a study subject ID (number). Each subject will be analyzed as randomized (ie, according to the vaccine regimen to which the subject was randomized).

**Exposed Population:** All subjects who receive at least one study vaccination.

**Safety Population:** All subjects in the Exposed Population who provide safety assessment data. This generally includes any subjects not lost to follow-up at Day 1, as they will be at risk for reporting an SAE. Each subject will be analyzed as treated (ie, according to the vaccine regimen a subject received, rather than the vaccine regimen to which the subject may have been randomized).

**Immunogenicity Evaluable Population:** For this Phase 1/2 study, the immunogenicity population will be analyzed as treated (ie, according to the vaccine regimen a subject receives, which may be different from the vaccine regimen to which the subject is randomized in the case of treatment errors). The Phase 1 subjects aged 18 to 49 years are not included in this population.

The Immunogenicity Evaluable Population (IEP) includes all subjects in the Exposed Population who:

- Have no major protocol deviation that would impact immunogenicity assessment or other reason to be excluded as defined prior to unblinding or analysis.
- Have not received a prohibited medication or vaccine.
- Provide evaluable serum sample results for baseline, the relevant post-vaccination time points, and within the required time frames:
  - Baseline: Day 1 or within 30 days before study vaccine administration
  - Day 29: Day 26 through Day 34, inclusive

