6.2.3. Adjustments for Covariates

The randomization for Phase 1 Cohort will not be stratified.

[figure not shown]
The randomization for Phase 2 Cohort will be stratified by age group (50-59, 60-64).

Immunogenicity analyses:

- For the Analysis of variance (ANOVA), study site will be included as fixed effect in the model.
- For the Analysis of covariance (ANCOVA) and the logistic regression, study site will be included as fixed effect and the log baseline titer will be included as covariate in the model.

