6.6.1. GMT/GMC, GMR and GMFR

To estimate the immunogenicity response 1 month first vaccination, OPA titers (log10) and IgG titers (mcg/mL) measured at Day 29 visit will be logarithmically transformed for analysis and GMTs/GMCs will be computed with 95% CI for each assay using ANOVA and ANCOVA.

[figure not shown]
- [S] [E] First model in an ANOVA with log10-transformed concentrations/titers at Day 29 as the dependent variable and treatment group and study site as the fixed effects in the model. Bar plots of OPA GMT, IgG GMC and their 95% CI computed by this model will be created for the full IEP only.
- [S] [E] Second model in an ANCOVA with log10-transformed concentrations/titers at Day 29 as the dependent variable, treatment group and study site as the fixed effects and log10 baseline concentration/titer as the covariate

The least squares means, and their 95% CIs calculated based on the ANOVA and ANCOVA will be back transformed and reported as the group GMT and GMC values. Comparisons between relevant groups will be based on the estimated adjusted GMTs measured at Day 29 visit for 24 serotypes in VAX-24 (of those 20 in PCV20), and mean square error calculated from the basic ANOVA model using contrast statements. The main comparison of interest will be the three VAX-24 dose levels group versus the PCV20 (20 serotypes) group. However, the three VAX-24 dose groups will also be compared in a pairwise fashion on a serotype-by-serotype basis. No adjustment for multiplicity will be applied and missing data will not be imputed. GMRs will also be calculated from the ANCOVA and ANOVA models.

The analysis of GMFR at Day 29 relative to Day 1 will also be computed using similar models:

- [E] First model in an ANOVA with log10-transformed fold ratio at Day 29 as dependent variable and treatment group and study site as the fixed effects in the model. A Forest Plot summarizing the results by serotype of this model will be created for OPA on the full IEP only.
- [E] Second model in an ANCOVA with log10-transformed fold ratio at Day 29 as dependent variable, treatment group and study site as the fixed effects and log10 baseline concentration/titer as the covariate

The least squares means, and their 95% CIs calculated based on the ANOVA and ANCOVA will be back transformed and reported as the group GMFR value.

[REDACTED]

[REDACTED]

[REDACTED]

[REDACTED]

[REDACTED]

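### The main-table GMT/GMC comparisons use a model without baseline titer or age stratum, although the protocol says response is correlated with baseline antibody

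*Protocol*

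**What the plan says.** Protocol 9.7.1 calls an ANOVA of log10 titer on treatment group and study site the primary model: "The results included in the main tables of this report will be based on this basic ANOVA model". An ANCOVA that adds log10 baseline titer is a secondary analysis. The stated rationale for including "baseline values as a covariate is that prior data have shown vaccine response is correlated with baseline antibody levels". GMRs are to be calculated from both models.

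SAP 6.6.1 repeats the two models as first and second, without ranking them. It takes one figure from the ANOVA for Day 29 levels: "Bar plots of OPA GMT, IgG GMC and their 95% CI computed by this model will be created for the full IEP only". The GMFR forest plot comes from the corresponding ANOVA on fold ratios.

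The Immunogenicity Evaluable Population (IEP), which is the primary immunogenicity set in SAP 4.1, is limited by Protocol 9.4 to subjects who "Provide evaluable serum sample results for baseline, the relevant post-vaccination time points, and within the required time frames".

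Protocol 5.8 and SAP 2.3 and 6.2.3 stratify the Phase 2 randomization by age, 50-59 and 60-64. SAP 6.2.3 then lists the model terms. The ANOVA has site. For the other models: "For the Analysis of covariance (ANCOVA) and the logistic regression, study site will be included as fixed effect and the log baseline titer". Age is not a term in any of them.

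On group contrasts, the protocol says: "Comparisons between relevant groups will be based on the estimated adjusted GMTs measured at Day 29 for 24 serotypes in VAX-24". In both documents that sentence goes on to name the error term; in the SAP's words, "and mean square error calculated from the basic ANOVA model using contrast statements".

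**The concern.** The protocol gives the reason for adjusting for baseline and then puts the unadjusted model in the main tables, with no reason for that order. Every IEP subject has a baseline result, so the ANCOVA loses nobody in the primary set. If baseline predicts Day 29 titer, the ANOVA leaves that variation in the error term, and chance baseline differences between arms pass into the GMR.

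Two smaller points follow. The only Phase 2 stratification factor is missing from every model. The contrast sentence can also be programmed in two ways. If *adjusted* means baseline-adjusted ANCOVA means, the estimate comes from one model and the error from another. If it means site-adjusted ANOVA means, the sentence is coherent. In Protocol 9.7.1 the only other use of the word for GMTs refers to the ANCOVA, and the SAP drops that parenthesis, so the text does not settle it.

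At stake is the precision of the serotype-by-serotype GMRs that compare three doses with PCV20 and with one another, above all in the 60-64 subgroup, whose planned minimum is 25 per arm.

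**Working it through.** **No plan figure to reproduce.** Protocol 9.1 gives no statistical basis for the Phase 2 sample size, and neither document states an SD, a correlation or a target precision for the GMRs.

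**Inputs from the documents:** 200 per arm in Phase 2; at least 100 of 800 subjects aged 60-64, or 25 per arm; 1:1:1:1 allocation; 95% intervals; baselines below LLOQ set to 0.5×LLOQ for GMTs (SAP 5.2).

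**Assumed:** SD 0.7 log10; baseline/Day 29 correlation r = 0.3, 0.5 or 0.7; 10 sites in simulations (the protocol synopsis says approximately 10); Day 29 difference between age strata d = 0.1 to 0.3 log10.

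**1. Interval width, ANOVA relative to ANCOVA.** ANCOVA residual variance is SD²(1−r²), so the ratio of log-scale widths is 1/√(1−r²). The censored columns are simulated (1,500 trials each). The last column is 200/(1−r²).

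| r | No baseline below LLOQ | 30% below | 50% below | 70% below | ANOVA n per arm matching ANCOVA at 200 (none below LLOQ) |
|---|---|---|---|---|---|
| 0.3 | 1.048 | 1.043 | 1.038 | 1.029 | 220 |
| 0.5 | 1.155 | 1.137 | 1.118 | 1.088 | 267 |
| 0.7 | 1.400 | 1.342 | 1.282 | 1.204 | 392 |

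**2. The 95% CI in fold terms.** The GMR is divided and multiplied by 10^(1.96 × SD × √(2/n)), with SD replaced by SD√(1−r²) for the ANCOVA.

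- n = 200, ANOVA: 10^(1.96 × 0.7 × 0.1) = 10^0.137 = 1.37. ANCOVA: 1.35, 1.32 and 1.25. Simulation (4 arms, 10 sites, 4,000 trials per r) gives 1.374 against 1.354, 1.317 and 1.255.
- n = 25, ANOVA by formula: 10^(1.96 × 0.7 × 0.283) = 2.44. Simulation (5,000 trials), which also carries the cost of estimating site effects and the t quantile, gives 2.59 against 2.49, 2.29 and 1.98.
- Simulated ANOVA coverage was 0.945 to 0.954, so that model is valid.

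**3. Chance baseline imbalance.** A one-standard-error difference in baseline moves the ANOVA GMR by 10^(r × SD × √(2/n)), taking equal SDs at both visits. With r = 0.5 this is 10^0.035 = 1.08 at 200 per arm and 10^0.099 = 1.26 at 25 per arm.

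**4. Age stratum.** With p = 100/800 = 0.125, the width saved by adding the term to the ANCOVA is √(1 + p(1−p)d²/(SD²(1−r²))) − 1.

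- d = 0.1, r = 0.3: √(1 + 0.109 × 0.01/0.446) − 1 = 0.12%.
- d = 0.3, r = 0.7: √(1 + 0.109 × 0.09/0.250) − 1 = 1.95%.

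**5. Contrast sentence.** If ANCOVA means are paired with the ANOVA error, coverage is 2Φ(1.96/√(1−r²)) − 1 = 0.960, 0.976 and 0.994 (simulated 0.953, 0.979 and 0.993). If both come from the ANOVA, coverage is 0.95.

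**The case against.** The case for leaving the plan alone is that both models are prespecified and both sets of GMRs will be reported, so only the choice of main table is in question. Immunogenicity is secondary, and the documents state no margin, power or success rule for the GMR. The one stated superiority rule, in Protocol 9.7.2, uses a logistic model that already contains baseline. All of this is true. It limits the importance of the point but gives no reason to lead with the less precise analysis.

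The size is assumed. At r = 0.3 and 200 per arm the interval factor moves only from 1.37 to 1.35, and the 40% figure needs r = 0.7 with no censored baselines. The 25 per arm is a floor, not an expected size. This also stands, and is why a range is shown.

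The age term gains almost nothing, and separate analyses by age group are planned. That is correct; its value is agreement with the randomization.

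A contrast statement normally takes estimate and error from one fit, so the mixed reading would need deliberate hand calculation, and its error is conservative. The sentence is therefore ambiguous, not a contradiction, and naming the model resolves it.

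The width figures do not apply to the GMFR forest plot, whose outcome is already a ratio to Day 1. For the four serotypes that PCV20 lacks (2, 9N, 17F, 20B), the baseline slope may differ between arms, so the stated gains may not describe them. A simulation with unequal assumed slopes gave ANCOVA coverage of about 95.5% to 98%, which is conservative.

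**Conclusion.** The concern holds as a matter of efficiency and clarity. The planned ANOVA is unbiased with correct coverage, but the main tables and the GMT/GMC bar plots would show the less precise of two planned analyses. With an assumed SD of 0.7 log10 and r between 0.3 and 0.7, ANOVA intervals are 5% to 40% wider, or 3% to 20% wider if 70% of baselines are below LLOQ. In absolute terms the loss is largest at the 60-64 minimum of 25 per arm. Omitting the age stratum costs about 0.1% to 2% of width. The contrast sentence leaves the model behind the adjusted GMTs open: one reading gives 95% coverage, the other about 96% to 99%. The change is worth making because it is nearly free, not because the planned analysis is invalid.

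**What to change.** - Make the ANCOVA with treatment, site, log10 baseline and age stratum the main model for the 50-64 GMT/GMC and GMR tables and for the GMT/GMC bar plots. Keep the ANOVA as supportive.
- State that each contrast takes both its estimate and its mean square error from that model.
- Add the age stratum to the logistic regression, and omit it from the separate 50-59 and 60-64 models.
- Record the change in SAP section 7, which now reports no departures from the protocol analyses.
- If the ANOVA stays as the main model, at least name the model from which the adjusted GMTs come.

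The cost is SAP wording, one added term and a swap of which planned model feeds the main tables; no extra data are needed. There are two small downsides. Headline GMTs become baseline-adjusted. In the supportive Exposed Population, where missing data are not imputed, the ANCOVA drops subjects without a baseline sample while the ANOVA keeps them.

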### **9.7.2 Threshold analyses**

For the 4 non-PCV20 serotypes that are in VAX-24, the % of subjects with a  $\geq$  4-fold increase in OPA titer will be evaluated using a logistic regression model, with an indicator variable for achieving a  $\geq$  4-fold increase in OPA titer as the dependent variable, and treatment group and study site as fixed effects and  $\log_{10}$  baseline titer as a covariate. The difference in proportions achieving a  $\geq$  4-fold increase in OPA titer in each of the three VAX-24 dose levels group versus the PCV20 and the corresponding 95% CIs will be calculated. If the lower bound of the 95% CI is  $> 0.1$ , the VAX-24 dose will be deemed statistically superior to PCV20.

The percentage of subjects achieving specified thresholds (eg, GMFR  $\geq 4$  in serotype-specific OPA and IgG, achieving OPA titer of at least serotype-specific LLOQ of the assay), and associated Wilson (score) 95% CI, will be calculated for the Day 29 visit data for each treatment group. A reverse cumulative distribution curve will be provided. Differences between pair-wise treatment groups may be determined via Fisher's exact tests.

### **9.8 Defined Safety Evaluation**

A defined safety evaluation will be conducted for the Phase 1 cohort of subjects aged 18 to 49 years, based on the safety data collected through Day 8. The results will be reported to the DMC by treatment group preserving the double-blind status on the subject level, unless the DMC requests unblinded individual treatments. After the interim safety analysis and DMC concludes that no safety concerns exist, the study will resume enrollment of subjects aged 50 to 64 years.

## 10 ADDITIONAL INFORMATION

### 10.1 Ethical Conduct of the Study

The study will be performed in accordance with the protocol and consistent with ICH GCP Guidelines and applicable local regulatory requirements and laws.

### 10.2 IRB Oversight

The study (protocol, informed consent form, recruiting materials, and any documents seen by the subject) will be reviewed and approved by an IRB appropriate to each study site. Subjects will not be recruited, consented, screened, or enrolled until the IRB has approved the required documentation. In addition, the IRB will review amendments to the protocol before their implementation.

The Investigator will retain all correspondence with the IRB in the trial master file and forward copies of all IRB approvals to the Sponsor.

### 10.3 Informed Consent

The Sponsor or designee will provide a master ICF template to each site for development of a site-specific ICF. At the Investigator's discretion, the site may develop a separate ICF for pre-screening as described in [Section 5.2](#).

All site-specific ICFs must be approved by the Sponsor or designee and the IRB and must be in compliance with ICH GCP, local regulatory requirements, and legal requirements. The Sponsor or designee will advise the Site of required changes to the master ICF template during the course of the study.

The Investigator will ensure that each potential study subject is fully informed about the nature and objectives of the study and possible risks associated with participation. Before informed consent is obtained, the Investigator, or a qualified person designated by the Investigator, will provide the potential study subject with ample time and opportunity to inquire about the details of the trial, and will answer all relevant questions to the potential study subject's satisfaction. The potential study subject will then decide whether or not to participate in the trial. The Investigator, or a qualified person designated by the Investigator, will obtain written informed consent from each study subject before any study-specific activity is performed.

The Investigator will retain the original and any amended signed and dated Informed Consent Form(s) at the study site and provide a copy to each study subject.

## **10.4 Subject Confidentiality**

The Investigator will ensure that each subject's anonymity is maintained. In all documents submitted to the Sponsor and/or its designee, subjects can be identified by subject ID number and initials. Documents not intended for submission to the Sponsor and/or its designee (eg, signed ICFs) must be maintained by the Investigator securely and must be in compliance with all federal laws and regulations and ICH GCP Guidelines.

